Wellness Control Intervention and Facilitators. We will utilize a Wellness program for the comparison group because this approach has been successfully used in other studies conducted by our team, including a pilot feasibility study conducted with Veterans with PTSD³⁶⁻³⁸. The Wellness intervention will be based on the VA Whole Health Program which helps individuals identify and achieve their personal health goals. The Whole Health Program include modules that address physical activity, personal development, healthy eating and drinking, stress management, relationships, personal surroundings, and spirituality. The Wellness intervention has been adapted with updated information from the VA Whole Health website and other resources to make it suitable for a population with PTSD and chronic pain. Using the SMART goals model, participants will set health and wellness goals each week, and discussions about ways to address potential barriers will be included in this condition. This group will be facilitated by doctoral level psychology staff, and/or psychology trainees and research staff who will be supervised by licensed and credentialed study staff.

For both interventions, study staff will hold "tech sessions" with participants prior to the initial session to ensure that audio and video connections are adequate, and participants know how to navigate the VA-approved videoconferencing platform used (e.g., Cisco Webex or Microsoft Teams). In addition, participants randomized to the Tai Chi group will have the opportunity to provide updates on any physical issues or limitations they would like to make the instructor aware of. Study staff will be available by telephone to help with connectivity

[figure not shown]
and technical issues at the beginning of each session and will call participants who have not logged in to offer assistance.

Participants may be given a water bottle after attending Tai Chi or Wellness class. The water bottles have a logo that says “VA Boston Health & Wellness Research” and display the circular VA emblem. These water bottles may be mailed to participants with a thank you note from the study team.

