Participants in both conditions will receive assessments at baseline and at 12 weeks (post-intervention). Participants in Phase Two (described below) will also receive a 3-month follow-up assessment. Weekly measures will be administered electronically using Qualtrics and entered into a secure database. (Please see section 5.5 below for more information about assessments). In addition, participants will receive phone calls each week where they will report on their home practice in the Tai Chi Group, and report on their SMART goals in the Wellness group. During these calls, participants will have the opportunity to provide feedback that may be used to improve their group experience. This could include topics such as: best ways to maximize telehealth visibility and at-home Tai Chi setup; any feedback to relay to the instructor including updates on physical issues or limitations; preferences for the amount of sitting vs. standing for the class; preferences for the amount of group discussion vs. didactic instruction, etc. This information will be recorded in an Excel spreadsheet that will use subject ID identifiers only and will be saved to a previously approved folder in the Drive: “[\\r04bhsnas61\resgroups\\$\\PTSD\\DATA\\RESEARCH\\TeleHealth - [name]\\Tai Chi Studies\\1.NCCIH_R34](\\r04bhsnas61\resgroups$\\PTSD\\DATA\\RESEARCH\\TeleHealth - [name]\\Tai Chi Studies\\1.NCCIH_R34)”. Information will be discussed at weekly lab meetings to help the study team improve the TeleHealth experience for group participants.

[figure not shown]

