While the risks of both the Tai Chi and Wellness group protocols are minimal, there are some potential risks. There is potential for minor injury from the Tai Chi exercises, including muscle tears, strain, sprains, and joint pain. In the Wellness Group Condition, some individuals may feel discomfort discussing goals with other participants and staff. In addition, participants may feel some stress, frustration, or boredom while completing the questionnaires. There will be a mental health professional available throughout the study for participants to talk with if needed. The social risks of participating in this protocol are minimal. There may be some embarrassment as participants learn to do Tai Chi or share in a group with other participants, but the instructors will be trained to be very sensitive to the individual needs of each participant and create an environment that feels safe and nonjudgmental. There is no economic risk associated with participating in this study.

Some discomfort may occur when discussing traumatic experiences during the assessment interviews. [name] are all licensed psychologists with extensive experience in handling emotional discomfort and risk management of patients with psychological disorders. They will directly supervise the study staff who will be conducting diagnostic interviews and one of them will always be on call when interviews are taking place to handle emergencies, such as safety concerns.

Protection Against Risk

- Given that this study will take place fully remotely, it will be important to ensure that participants have a safe and private location where they will be able to participate in the study. In order to protect the confidentiality of everyone in their group, participants will need to be in place where others are not able to see their video screen or hear the audio.

- Study staff will monitor participants on screen (grid view) during the classes, direct them to stay in front of their cameras, and take appropriate actions (e.g. calling out to them, calling by phone) if participants are not visible on screen.
- Participants will also need to provide the address where they will be participating in the study, and contact information of someone who can be called in the event of an emergency. The local police number will also be obtained for emergency purposes

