- Participants will be informed in the ICF that “*to comply with laws and regulations, we may need to share safety-related information such as that relating to child abuse or neglect; elder or disabled person abuse; specific reportable diseases; harm to yourself or others*”. Although there will be no questions asked in the assessments regarding suicidal or homicidal thoughts or intentions, if suicidal or homicidal intentions are disclosed, confidentiality may be broken in order for protective measures to be taken. Although there will be no questions asked in the assessments regarding care of children or geriatric persons, if a participant were to disclose child or elder abuse, appropriate agencies would be contacted, and participants will be so informed in the consent form.
- All personnel involved in this proposed project will have completed the required ethics, human subjects, and confidentiality training, which include information about maintaining data integrity and security. Careful monitoring of participants during all phases of study participation will be conducted by the project staff. Participants will be instructed to contact study personnel at any time (including during the follow-up interval) in the event of worsening of symptoms. Participants who begin treatment and experience adverse outcomes sufficient to require removal from the study will receive appropriate clinical care.
- [name] are all licensed psychologists with extensive experience in handling emotional discomfort and risk management of patients with psychological disorders. They will directly supervise the study staff who will be conducting screening interviews, assessments, and intervention sessions. One of the psychologist investigators will always be on call during interactions with study participants to handle emergencies, such as safety concerns, and to make appropriate referrals for mental health services. Participants who are screened out due to recent suicide attempts or active suicidality will be referred for appropriate VA mental health services.

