If we are successful in recruiting more than 12 Veterans over the recruitment push, we may randomize up to 20 Veterans to help ensure that we will end up with an average of 12 Veterans who are able to participate in the groups. Random assignments to condition will be managed by study staff who will generate the randomization scheme. Participants will be randomized in order of completion of initial telephone screening.

Study staff will then call participants to inform them of their condition assignment and the days and times of the group intervention to which they have been assigned.

AIM 1. During Phase One, we will refine and standardize two treatment protocols for Veterans diagnosed with PTSD and chronic musculoskeletal pain. Tai Chi and Wellness interventions will be adapted for delivery via a videoconferencing platform for the population.

Using information gathered from group and individual feedback sessions, we will edit and refine the participant manuals to optimize remote delivery issues such as sound quality, ability to see and follow instructors, instructor ability to view Veterans, and connectivity difficulties. We will also inquire about frequency, duration, and time of day of sessions, class size, ease of use of printed materials and log sheets. We will use adherence and satisfaction data and qualitative feedback to modify the interventions and improve the protocol before moving to *Phase Two*.

AIM 2. During Phase Two, we will determine the feasibility and acceptability of a remotely delivered randomized trial of the two interventions and the assessment protocols.

Feasibility and acceptability will be quantified by evaluating rates of eligibility, enrollment, satisfaction, adherence, retention, and credibility expectancy, and compliance with home practice. Specifically:

- Successful eligibility and enrollment will be indicated by our ability to meet overall recruitment goals (in addition to successfully recruiting a representative sample of women and minorities as projected in the Enrollment Table).
- Treatment satisfaction will be indicated if at least 70% of participants have a score of 3 or greater (corresponding to mostly or very satisfied) on the 1-4 scale of the CSQ.
- Adherence and retention will be determined by meeting the metric of at least 75% of participants attending at least 70% of the treatment sessions and 70% of participants completing all baseline and follow-up assessments.

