5.0 Reporting

Monitoring of safety and data quality in the proposed study will be the responsibility of all personnel on the project, under the guidance and supervision of the Principal Investigators, and with the oversight of an Independent Safety Monitor, [name]. [name] is an expert in the field of pain management and behavioral medicine from VA Boston Healthcare System and Boston University Chobanian and Avedesian School of Medicine. He has a strong track record of conducting research on non-pharmacological pain management interventions and has worked with and developed interventions for Veterans with co-morbid pain and PTSD. Given his experience in working with the specific population we will be recruiting for this study, and his expertise in non-pharmacological interventions for pain and PTSD, he will be an ideal Independent Safety Monitor for this study. [name] will review our participant safety processes upon initiation of the study and will assess the progress of this study at least once a year. This will include evaluating the processes that are delineated below.

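### The plan describes no scheduled adverse-event question, and no harm summary enters the Phase One to Phase Two step or the feasibility criteria

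*Combined protocol and SAP*

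**What the plan says.** **Risk.** Section 4.1 (Risks to Human Subjects) states: "There is potential for minor injury from the Tai Chi exercises, including muscle tears, strain, sprains, and joint pain".

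**How problems come to light.** The weekly call described in section 4.1 takes home practice (Tai Chi) or goals (Wellness). It also offers room for feedback, one example of which is "any feedback to relay to the instructor including updates on physical issues or limitations". On storage: "This information will be recorded in an Excel spreadsheet that will use subject ID identifiers only". On use: "Information will be discussed at weekly lab meetings to help the study team improve the TeleHealth experience for group participants". Under Protection Against Risk, section 4.1 adds on-screen watching of classes, a general promise of careful monitoring by project staff in all phases, and this: "Participants will be instructed to contact study personnel at any time (including during the follow-up interval) in the event of worsening of symptoms". Section 4.5 has everyone complete the PCL-5 and BPI weekly during the intervention in both phases, and gives the purpose as gauging burden.

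**Reporting.** Section 5.0 adopts the FDA definitions of AE and SAE. Staff must report all AEs and SAEs at once to a principal investigator, who reports them to the IRBs. Any SAE goes to the VA IRB within 5 days, and a yearly AE/SAE summary accompanies the VA IRB renewal. The Independent Safety Monitor reviews safety processes at initiation and "will assess the progress of this study at least once a year".

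**Decisions.** For the move between phases, section 4.7 (Aim 1) says: "We will use adherence and satisfaction data and qualitative feedback to modify the interventions and improve the protocol before moving to" Phase Two. The Aim 2 list covers eligibility, enrolment, satisfaction, adherence, retention, credibility and home-practice compliance.

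**The concern.** This is a first test of a physical intervention done at home by people enrolled because they have chronic musculoskeletal pain, and the protocol itself names strains, sprains and tears as risks. A feasibility trial of that kind would normally give a plain account of harms, and reviewers of the later efficacy trial would expect one.

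As written, three links are missing. No instrument or scheduled question asks about AEs. A physical problem mentioned on the call has a stated destination, the feedback sheet, but no stated route to AE assessment. And whatever is recorded is not among the inputs to either decision the trial must make: whether and how to move to Phase Two, and whether the approach is feasible. At stake is a feasibility conclusion reached without usable harm data. A pattern seen in Phase One would also have no scheduled independent review before Phase Two begins.

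**Working it through.** The plan contains no harm figure to reproduce. Its only precision statements concern the feasibility metrics in section 4.7. Exact (Clopper-Pearson) 95% limits give 26/36 = 72.2% (54.8% to 85.8%), matching the stated 72% (55% to 86%). For 28/36 they give 77.8% (60.8% to 89.9%), which is the stated 77% (60% to 89%) apart from truncation. Neither figure bears on harms, so the main check is documentary.

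**1. What each capture route covers**
- On-screen watching (4.1) covers live classes. It does not cover home practice, nor practice from the video after a missed session.
- Careful monitoring (4.1) has no instrument or schedule attached.
- Participant-initiated contact (4.1) depends on the participant deciding to call.
- Weekly BPI and PCL-5 (4.5) are solicited from everyone, but no review for worsening is described. In a chronic-pain sample a pain score does not identify a new injury or its cause.
- Feedback interviews (4.1, 4.5) come after treatment and yield themes and quotations, not counts.
- The weekly call (4.1) is the one regular staff conversation that could reach home practice, and physical issues raised there are logged as feedback.
- The measures tables in 4.5 contain no AE form, scheduled AE question or recall period.

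**2. What feeds the decisions (4.7)**
- Phase One to Phase Two: adherence, satisfaction and qualitative feedback.
- Aim 2: the seven items listed above, none of them a harm.
- Aim 3: preliminary data on feasibility, acceptability, adherence and burden.
- No AE summary by arm is planned.

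**3. Independent review (5.0)**
- The monitor's minimum is initiation plus once a year. No review is tied to the phase change, and the reporting text in 5.0 and 7.0 routes events to the investigators and IRBs without naming the monitor.

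**4. What the sample can show**
- Planned Tai Chi participants: 6 in Phase One; 3 cohorts × 6 = 18 in Phase Two; 24 in all.
- Exact two-sided 95% upper limit with zero events, 1 − 0.025^(1/n): 45.9% for n = 6, 18.5% for n = 18, 14.2% for n = 24.

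**5. Illustration of incomplete capture**

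The documents give neither an injury rate nor a capture fraction, so both are assumptions. With true rate p and capture fraction c, the chance of recording no event among 18 is (1 − pc)^18. At p = 10% the expected number of affected participants is 18 × 0.10 = 1.8, and:
- c = 100%: 0.90^18 = 15%
- c = 70%: 0.93^18 = 27%
- c = 50%: 0.95^18 = 40%
- c = 30%: 0.97^18 = 58%

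Varying the rate, with full capture: p = 5% gives 0.95^18 = 40%, and p = 20% gives 0.80^18 = 2%. At half capture these become 0.975^18 = 63% and 0.90^18 = 15%.

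**The case against.** The strongest reply is that the plan is far from silent on safety. All AEs, not only serious ones, must go at once to a principal investigator. The staff who make the weekly calls are under that same duty, so the feedback sheet does not replace AE reporting. Physical problems can also shape Phase Two informally through lab meetings and Phase One interviews, whose coding starts with categories that include negative experiences. This stands. It narrows the gap to a missing link rather than absent reporting. But a duty to report works only on events that staff learn of and recognise as AEs.

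Four stronger readings are tempting, and the documents do not support them.
- A reader might infer that harms are captured only when volunteered. On-screen watching, stated staff monitoring and the weekly scales contradict that.
- A reader might infer that capture differs by arm, because before the course "participants randomized to the Tai Chi group will have the opportunity to provide updates on any physical issues or limitations". That session precedes the first class, so it cannot record an intervention injury. The weekly-call feedback is offered to participants generally, and the scales are the same in both arms. Some feedback topics are specific to Tai Chi, but differential capture is not shown.
- A reader might infer that nobody independent sees Phase One events. SAEs reach the VA IRB within 5 days, and the monitor's yearly review is a minimum. What is true is that no monitor review is tied to the phase change.
- A reader might infer that the criteria omit harms because of how harms are recorded. They omit them because no harm item was written in, whatever the capture method.

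Two further points are fair. Even perfect capture gives no precise rate at these sizes. And the call script and interview guide are not among the documents, so a prompt there cannot be excluded; if one exists, the protocol should say so.

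**Conclusion.** The point holds as a gap in linkage and use, not as an absence of safety reporting. No scheduled AE question is described, call-reported physical issues have no stated path to AE review, and no harm summary is an input to the phase step or the Aim 2 criteria. No monitor review is tied to the start of Phase Two, when a target of 36 and up to 60 more Veterans enter, half of them (18 to 30) assigned to Tai Chi.

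This conclusion rests on the text alone. The zero-event probabilities are illustrations that depend on an assumed injury rate and assumed capture, and they treat participants as independent although classes are shared. Because zero events in 18 would still be compatible with a rate as high as 18.5%, any harm summary here can only be descriptive. The change is worth making because it is cheap and because events not asked about at the time cannot be reliably recovered later.

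**What to change.** 1. Add one scripted question to the existing weekly call, in identical words in both arms: any new or worsened injury, pain or distress since the last call, and whether it arose in class or in home practice.
2. Assess positive answers against the FDA definition already adopted in section 5.0, and enter those that qualify in the AE log as well as the feedback sheet.
3. In section 4.7, plan descriptive AE counts by arm with exact confidence intervals, reported beside the Aim 2 metrics, and list the Phase One AE summary among the inputs to the Phase Two step.
4. In section 5.0, send the Phase One AE/SAE summary to the Independent Safety Monitor before the first Phase Two randomisation, and copy the monitor on SAE reports when they go to the IRB.

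The cost is one question per call: 12 calls × 48 participants = 576 at target, or 12 × 80 = 960 at the recruitment ceiling. There are also short summaries to a monitor already appointed. The real downside is that a chronic-pain sample will generate more minor AE records, each falling under the plan's immediate-reporting duty, so staff time should be allowed for.

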4.2 Recruitment Methods

Participants will be recruited in the following ways:

1. IRB approved flyer and link to the study website may be posted on VA Facebook pages (e.g., Health Promotion Disease Prevention Facebook Page). Information contained in the approved flyer and posted on the approved website [https://www.research.va.gov/for_veterans/ptsd-pain-holistic.cfm] may be used by researchers, clinicians, or other interested parties outside VA Boston to inform populations of Veterans about this study (e.g., researchers of studies taking place at other VA sites, researchers at non-VA institutions, personnel from local or national Veterans organizations).
2. IRB approved flyer and webpage developed on a VA ORD website may be distributed at public events for Veterans and/or at public research affiliated events (e.g., Museum of Science Annual Brain Health Fair).
3. IRB approved language approved for the flyer and website may be used to promote the study in newsletters distributed by the VA.
4. IRB approved flyer may be posted throughout VABHS and Vet Centers.
5. Investigators will inform medical center staff about the study and encourage them to inform Veterans with symptoms of PTSD of the study or provide them with IRB-approved pamphlets.
6. We may utilize the National Center for PTSD's electronic referral database which consists of over 500 potential research participants. Participants are entered into the repository on a voluntary basis, and written permission for future contact has already been established. The IRB of the VABHS has approved this recruitment mechanism (IRB#1293: "Multiproject Subject Recruitment by the National Center For PTSD").
7. IRB approved flyer and link to the study website may be posted to Veteran social media platforms such as Veterans Facebook groups and pages. Our research team will contact the administrator of each page we wish to post to and inquire if they are willing to post the study flyers, brochures, and link. If yes, the approved recruitment materials will be shared.
8. Study staff may post directly to social media about research study. In addition to asking administrators of social media groups to post to pages and groups, study staff may announce the study on various Veteran social media platforms such as New England Friends of Veterans, Boston Veterans Collaborative and Veterans Facebook groups, directly. Our research team will post the IRB approved study flyer and link to our website. The study will continue to track the source of recruitment for each participant in order to evaluate and maximize recruitment strategies throughout the study. The ability to post directly will allow us to reach a wider audience as often the administrators miss the study team's requests to post.

If additional recruitment materials are developed in the future, we will submit those for IRB approval before employing them.

Study staff will contact potentially eligible Veterans by telephone and describe logistical aspects of the study. Interviewers will answer any questions and obtain oral consent for screening to inquire about inclusion and exclusion criteria. Participants who are not screened out will be scheduled for a remote informed consent and baseline assessment during which the remaining inclusion/exclusion criteria will be evaluated. At no time will study staff engage in "cold-calling" to contact potential participants.

To ensure success in meeting the target recruitment goal of averaging 6 participants per group (12 participants for Phase One and 36 participants for Phase Two), we will recruit up to 10 participants per group for a total of 20 participants for Phase One and 60 participants for Phase Two.

